[figure not shown]
[figure not shown]
ORGANIZATION OF DETAILED PROTOCOL

Title: Effects of contralesional repetitive magnetic stimulation combined with fluoxetine on motor recovery in stroke patients
Protocol #:2014P001046
Date: 08/10/2017

[figure not shown]

Aim 1: Determine whether low-frequency rTMS of the unaffected M1 associated with fluoxetine offers an additional benefit on motor function over pharmacotherapy (fluoxetine) alone after three months of the combined therapy. Our hypothesis is that low-frequency rTMS combined with fluoxetine will induce greater improvement in motor function as compared to sham rTMS and fluoxetine.

Sub Aim 1.1: As to control for the effects of spontaneous recovery, we will also assess whether the superior effects of the combined effects will be superior to spontaneous recovery by comparing the results of the two groups against a placebo group (placebo fluoxetine and sham rTMS). We hypothesize that both groups (combined treatment and fluoxetine alone) will have a superior effect as compared to placebo only.

Aim 2: Determine whether fluoxetine combined with rTMS results in additional positive modulation of motor cortex excitability and cortical plasticity as compared to fluoxetine alone. Our hypothesis is that active rTMS combined with fluoxetine will induce a greater increase in the amplitude of motor evoked potential and greater LTP-like (long-term potentiation) as indexed by PAS-25 of the affected hemisphere (M1) as compared to sham rTMS combined with fluoxetine.

V. SUBJECT SELECTION

We will recruit 45 patients with ischemic stroke. The desired sample size is calculated, with some assumptions, based on the amount of patients treated in Spaulding Rehabilitation Hospital and affiliate hospitals and clinics. The study eligibility criteria that will be used for this study are based on the FLAME trial (as we will investigate the additional benefits of combining fluoxetine with rTMS). We broadened the motor score criteria and time since stroke in order to significantly improve the impact of the study and improve our understanding of the mechanisms behind plasticity after stroke in a broad population.

Subjects will conform to the following criteria:

Inclusion Criteria:

- Ischemic infarction within the past 2 years post event that has caused hemiparesis or hemiplegia, as self-reported and/or confirmed by medical record.
- Older than 18 years old.
- Upper extremity weakness defined as a score of >11 and ≤56 on the arm motor Fugl-Mayer motor scale.
- Minimal pre-stroke disability defined as a score of <3 in the Modified Rankin Scale.
- Subjects need to be able to follow directions and participate in 2 hours of testing with short breaks.
- Subjects need to be able to provide informed consent.

[figure not shown]
Exclusion Criteria:

- Any substantial decrease in alertness, language reception, or attention that might interfere with understanding instruction for motor testing
- Excessive pain in any joint of the paretic extremity (not applicable to severe stroke subjects), as self reported
- Contraindications to single pulse TMS (will be used to measure cortical excitability) such as: history of seizures, unexplained loss of consciousness, any metal implants in the head, frequent or severe headaches or neck pain, any other electronic implanted medical devices such as pacemakers, defibrillators, or implant medication pump.

- Patients who are currently taking fluoxetine should accept a 5 week washout period before baseline (to be reconfirmed during baseline visit).
- Patients taking any other SSRI at the time of enrollment or in the previous month (the patients should accept a 5 week washout period before baseline to be reconfirmed during baseline visit).
- Patients taking any other medication likely to have adverse interaction with SSRIs (all the medications the patient is taking will be carefully reviewed, as noted below in "Monitoring of important drug interactions").
- Active depression on admission to SRH defined by a score of 24 or higher in the Hamilton Depression Rating Scale (HAM-D)
- Concurrent medical condition likely to worsen patient's functional status in the next 6 months such as: cancer, terminal heart, kidney or liver disease, as self-reported and/or confirmed by medical record.
- Pregnancy.

VII. STUDY OVERVIEW AND PROCEDURES

Study overview:

This study is a parallel, randomized, double blind, placebo controlled clinical trial. We will use the same duration and regimen of fluoxetine treatment as the FLAME trial as this trial showed that fluoxetine is efficacious when compared against placebo. Subjects will be randomized to one of three groups, where they will receive: 1) fluoxetine + active rTMS, 2) fluoxetine + sham rTMS or 3) sham rTMS + placebo fluoxetine. With a total of 45 patients, 15 patients will be randomized to each group using a computer based randomization program.

This study is structured in 3 visits where baseline and post intervention assessments will be collected, 10 daily stimulation sessions (from 3^{rd} until 12^{th} visit), and subsequently, subjects will return for a weekly stimulation session for the next 8 weeks (visit 14^{th} to 21^{th}). Last visit will be the 22^{nd} and the whole battery of assessments is going to be collected. A table of the study flow is presented below.

Protocol Details:

There will be ten stimulation visits (to be given over a period of 15 days), followed by weekly sessions of stimulation for the next 8 weeks. During each stimulation visit, rTMS equipment will be placed on the subject's unaffected hemisphere over the primary motor cortex (M1). They will receive either active or sham rTMS with fluoxetine – or sham rTMS and placebo. The 30 subjects randomized to receive sham rTMS will have the opportunity to enroll into an open label at the conclusion of their participation in the randomized portion of the trial. This will consist of 10 daily active stimulation sessions that can be carried out over the course of 2 weeks. Subjects will only receive rTMS and not the study drug, Fluoxetine.

Intervention Details:

Repetitive transcranial magnetic stimulation:

Low frequency rTMS stimulation (active stimulation)

• During this stimulation session, the participant will receive a session of low-frequency rTMS to the primary motor cortex of the unaffected cerebral hemisphere. The resting motor threshold (MT) of the first dorsal interosseous (FDI) in the affected and unaffected hemispheres will be measured. The participants will receive the rTMS over the area corresponding to the "hot spot" for stimulation as defined by motor threshold determination, as described by prior rTMS application studies (Rossini et al., 1994).

• Low frequency rTMS stimulation will be applied according to the following parameter: intensity of 100% MT, frequency of 1 Hz, 1200 pulses as a single, continuous train lasting 20 minutes. This intervention is associated with significant motor gains in chronic (Mansur, 2005)(Fregni, 2006) and acute stroke. In addition, it is a safer approach to be used in chronic stroke (Fregni review).

Sham rTMS stimulation:

• For sham rTMS stimulation, we will place the coil in the same location usually used for the active stimulation. We will also utilize the same stimulation parameters. However, we will replace the active coil with a sham coil to ensure no stimulation is actually provided.

Drug Intervention:

[figure not shown]
Fluoxetine:

- Subjects will receive fluoxetine 20 mg daily after enrollment during their baseline visit. They will take the study drug by mouth once daily from this day until the protocol is completed (for 90 days) we will use the same regimen as in the FLAME study.
- The drug will be dispensed by the pharmacy and nursing staff of Spaulding while subjects are inpatient at the hospital. Upon discharge from Spaulding subjects will be given the remaining pills in their prescribed amount supply and instructed to take one each day until finished.
- If the subject is discharged to a skilled nursing facility a copy of the protocol and contact information will be sent with the patient and the medication. Study staff will call the facility to answer questions and enlist support in continuing the study medication there. Study drug compliance will be monitored weekly via self-report measures either during a study visit or by phone. Subject's responses will be kept in a compliance log.
- If the subject is enrolled as outpatient a licensed physician on the study staff will dispense the medication to the subject during the baseline visit.

Placebo control:

• Subjects will receive a placebo pill daily after enrollment during their baseline visit. They will take the study drug by mouth once daily from this day until the protocol is completed (for 90 days). The placebo will be dispensed by the pharmacy and nursing staff of Spaulding while subjects are inpatient at the hospital. Upon discharge from Spaulding subjects will be given the remaining pills in their prescribed amount supply and instructed to take one each day until finished. The procedure for taking the study drug and to monitor for compliance will be the same as for the patients receiving the active drug.

www.randomization.com	

Clinical Assessments:

A rater blind to the treatment arm will administer the following:

- Jebson Taylor Hand Function Test (JTHF): This will be our primary outcome. This test
 was designed as a broad measure of hand function. It provides information on the time
 required for the subject to turn cards, pick up small objects, simulate feeding by picking up
 beans with a spoon, stack checkers, and lift empty and 500 g full cans (Jebsen et al., 1969).
 This instrument showed to be sensitive to measure motor changes induced by motor cortex
 stimulation (REVIEW marcel BJ). When performing a certain sub-task, if the subject
 demonstrates the inability to complete that task and verbally acknowledges he/she cannot
 perform, we will move on to the next task and score appropriately.
- 2. Fugl-Meyer motor scale (FMMS): This instrument was the main outcome used in the FLAME study and is widely used for assessment of motor recovery after stroke. (Gladstone et al, 2002).
- 3. Modified Ashworth Scale: This instrument is a 6-point rating scale that is used to measure muscle tone. This test is performed by moving the body part through the joint range of motion (ROM), with no specification as to the speed of the movement.
- 4. Beck Depression Inventory (BDI): This 21-item multiple-choice test measures the presence of and the degree of depression in adults.
- 5. Mini Mental State Examination (MMSE): The MMSE is a brief screening instrument used to assess cognitive abilities. We will be using this assessment as a baseline evaluation and a follow- up. Consistency of MMSE scores should suggest that a subject had no cognitive changes throughout the intervention period that may have affected test performance or carryover of the program.
- 6. National Institute of Health Stroke Scale (NIH SS): is a tool used to objectively quantify the impairment caused by a stroke. It is composed of 11 items, each of which scores a specific ability between a 0 and 4.
- 7. Visual analogue scale (VAS) for anxiety: This tool is a visual scale of 0-10 where the subject can rate their level of anxiety where 0 is no anxiety, and 10 is the worst anxiety that the subject has ever felt.
- 8. Visual Analogue Scale (VAS) for pain /comfort: This tool is a visual scale of 0-10 where the subject can rate their level of pain where 0 is no pain, and 10 is the worst pain that the subject has ever felt.
- 9. Side Effects / Adverse event tracking Questionnaire for rTMS: After each session, subjects will complete a questionnaire to evaluate potential common adverse effects rTMS (headache, neck pain, itching and redness at the site of stimulation) on a 5-point scale.
- 10. The Antidepresant Side-Effect Checklist (ASEC): The ASEC is a questionnaire that assesses the possible appearance of side effects related to the use of common antidepresants, their severity and if they are linked or not to the drug (Uher, 2010).
- 11. Blinding Questionnaire: to be performed at the end of the daily stimulation sessions and at the end of the weekly stimulation sessions.. This questionnaire will ask the rater and the subjects whether the intervention was sham or active rTMS. The confidence of these responses will be rated from 0 to 5 0 being no confidence and 5- total confidence. If the subject is interested in knowing what stimulation he/she received, the co-investigator may inform the subject when his/her participation in the trial has ended.

12. A log of the hours of therapy that patients are receiving and the meditations they are taking will be kept and updated every week.

Assessment of cortical excitability and plasticity – single and paired pulse TMS and PAS:

Aim 1: Determine whether low-frequency rTMS of the unaffected M1 associated with fluoxetine offers an additional benefit on motor function over pharmacotherapy.

We will investigate changes in cortical excitability by evaluating the motor evoked potential (MEP) and the resting motor threshold (MT) (with the same methods as in our previous study (Fregni et al., 2006b)). We will also measure intracortical excitability using the technique of paired-pulse, and interhemispheric differences using transcallosal inhibition. Both the affected and unaffected M1 will be studied.

We will investigate the resting motor threshold (measured following the technique described by (Rossini et al., 1994)) before and after stimulation. For the MEP study, we will initially adjust TMS intensity to achieve a baseline MEP in the first dorsal interosseous of about 1 mV peak-to-peak amplitude before intervention. Stimulation intensity will be kept constant for each subject throughout the experiment. The MEPs will be recorded and stored in a PC computer for off-line analysis. We will record 10 MEPs for each time point (immediately before and after the rTMS stimulation) and average their peak-to-peak amplitude and area-under-the-curve.

For the first aim, the primary outcome will be motor function changes as indexed by Jebsen Taylor Hand Function test and secondary outcome will be Fugl-Meyer motor scores. Differences between the two groups will be tested using Student's t-test and, in addition, we will adjust for important baseline variables and also test the time effect in general mixed longitudinal models. Secondary analyses will be conducted in an exploratory manner (no correction for multiple comparisons). [We will also conduct exploratory correlational analysis as to understand whether beneficial effects of the combined intervention (active rTMS and fluoxetine) are associated with any baseline characteristics as to explore potential predictors of the effects of treatment. This result may also be used along with results for aim 2 to understand the mechanisms of the combined treatment.]

[For subaim 1: the primary outcome will be motor function changes as indexed by Jebsen Taylor Hand Function test and secondary outcome will be Fugl-Meyer motor scores. We will conduct the same analysis as aim 1 (Differences between the two groups will be tested using Student's t-test with adjustment for covariates) but in this case we conduct two comparisons (real rTMS+fluoxetine vs. sham rTMS+placebo fluoxetine and sham rTMS+fluoxetine vs. sham rtMS+placebo fluoxetine)]

For the second aim, we will initially build a mixed ANOVA model in which the dependent variable will be the parameters of cortical excitability and plasticity (PAS) indexed by

neuropsychological measures. The independent variables will be group [(active and placebo control)], time and the interaction group/time. [If we find a significant interaction effect between group and time, we will confirm our hypothesis that TMS induces a significant differential plasticity when compared to fluoxetine alone. Furthermore we will conduct additional analysis in which we will change the groups in the variable group (real rTMS+fluoxetine vs. sham rTMS+placebo fluoxetine and sham rTMS+fluoxetine vs. sham rtMS+placebo fluoxetine)

	·

Adeyemo, B. O., Simis, M., Macea, D., & Fregni, F. Systematic Review of Parameters of Stimulation: Clinical Trial Design Characteristics and Motor Outcomes in Noninvasive Brain Stimulation in Stroke. *Frontiers in Psychiatry*, *3*, 8.

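### Aim 1 leads with an unadjusted t-test on 15 patients per arm from a very mixed population, and the plan does not name its covariates or say whether the adjusted or unadjusted result decides.

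*Combined protocol and SAP*

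**What the plan says.** **Population.** Section V, Subject Selection, admits "Ischemic infarction within the past 2 years post event", with no lower limit on time since stroke, and arm Fugl-Meyer scores above 11 and up to 56. The breadth is intended: "We broadened the motor score criteria and time since stroke in order to significantly improve the impact of the study". The intervention section provides for both inpatients and outpatients.

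**Size and allocation.** "We will recruit 45 patients with ischemic stroke", and under Study Overview "15 patients will be randomized to each group using a computer based randomization program". The basis for the size is availability: "The desired sample size is calculated, with some assumptions, based on the amount of patients treated in Spaulding Rehabilitation Hospital". The only other visible allocation text is an isolated line, "www.randomization.com", between the placebo paragraph and Clinical Assessments.

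**Spontaneous recovery.** Sub Aim 1.1 adds a group on placebo and sham stimulation, introduced with "As to control for the effects of spontaneous recovery".

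**Analysis.** The text for the first aim makes change in JTHF the primary outcome and continues: "Differences between the two groups will be tested using Student's t-test and, in addition, we will adjust for important baseline variables". The same sentence adds longitudinal mixed models. The sub-aim text says it repeats the Aim 1 analysis, but describes that analysis as a t-test that adjusts for covariates. Neither paragraph lists the covariates, mentions time since stroke as one, or says which result carries the conclusion.

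**The concern.** Time since stroke and initial severity are plausible predictors of how much a patient's hand function will change without any effect of treatment. The protocol recognises spontaneous recovery and answers it with a concurrent placebo group. That works on average over repeated randomisations. In the one trial that will be run, with 15 patients per arm, it works only as well as the arms happen to be matched.

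Two things are at stake. First, if the arms differ by chance on a prognostic factor, an unadjusted comparison carries that difference into the treatment estimate. Second, because the plan offers an unadjusted result, an adjusted result with an open covariate list, and a mixed model, the choice among them could be made after the data are seen. Neither of the two descriptions of the Aim 1 analysis settles it.

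**Working it through.** **The plan's own figures.** 3 arms × 15 = 45, and 2 sham-stimulation arms × 15 = 30. Both agree with the text. The size itself cannot be rebuilt, because no alpha, power, effect size or SD is given. For scale, at two-sided alpha 0.05 and 80% power (assumptions), 15 per arm detects a standardised difference of about 1.02 by the normal approximation, (1.96 + 0.84) × √(2/15), or 1.06 with the exact t distribution.

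**Step 1: how often the arms differ at baseline.** For a continuous factor measured in SD units, the chance difference between two arms has SD √(2/15) = 0.365.

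| Event | Probability |
|---|---|
| Two given arms differ by more than 0.25 SD | 49% |
| Two given arms differ by more than 0.5 SD: P(\|Z\| > 0.5/0.365) | 17% |
| Two given arms differ by more than 0.75 SD | 4% |
| Some pair of the three arms differs by more than 0.5 SD | 36% |

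For a yes/no factor such as early after stroke, held by 20% to 50% of patients (assumption), two given arms differ by 4 or more patients of 15 in 11% to 20% of trials.

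**Step 2: what this does to the test.** The shift in the unadjusted estimate is the covariate-outcome correlation times the imbalance. At an imbalance of 0.5 SD, correlations of 0.3, 0.5 and 0.7 (assumptions) give 0.15, 0.25 and 0.35 SD. Simulation of 100,000 two-arm trials per setting, with no treatment effect and one normal covariate, gives these rejection rates:

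| Correlation | t-test, all trials | t-test, imbalance > 0.5 SD | ANCOVA, imbalance > 0.5 SD |
|---|---|---|---|
| 0.3 | 4.9% | 7.6% | 4.9% |
| 0.5 | 5.0% | 11.7% | 5.1% |
| 0.7 | 5.0% | 17.7% | 5.0% |

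With a true effect of 1.06 SD, power is about 80% for the t-test and 82%, 89% and 97% for ANCOVA on that single covariate.

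**Step 3: precision with the three covariates proposed below.** If they explain a share R² of outcome variance, the residual variance falls by the factor 1 − R². Estimating k normal covariates costs on average a factor 1 + k/(ν − k − 1), where ν is the within-arm degrees of freedom. The effective number per arm is 15 / [(1 − R²) × that factor].

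- Two arms only: ν = 28, k = 3, factor 1 + 3/24 = 1.125. R² = 0.1 gives 15/(0.9 × 1.125) = 14.8. R² = 0.4 gives 15/(0.6 × 1.125) = 22.2.
- All 45 patients: ν = 42, factor 1 + 3/38 = 1.079. R² = 0.1 gives 15/(0.9 × 1.079) = 15.4. R² = 0.4 gives 15/(0.6 × 1.079) = 23.2.

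Simulation agrees: 14.8 and 22.1 for two arms, 15.4 and 23.0 for three.

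**The case against.** The strongest reply is that the plan already adjusts. The sentence that names the t-test goes on to baseline adjustment and mixed models, the sub-aim wording has covariates in the test itself, and being named first does not make the unadjusted result decisive. This stands, so it would be wrong to say that no adjustment is planned. What remains is that the covariates are open and the deciding model is not stated.

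Second, chance imbalance is ordinary sampling error, and the t-test's standard error already allows for it. This also stands. A reader might infer that the comparison is biased or its false-positive rate inflated. The overall rate is 5%. The 17% and 36% in Step 1 are frequencies of imbalance, not of false positives. The excess in Step 2 is conditional on an imbalance having occurred.

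Third, because the outcome is a change score, the starting level of JTHF is partly accounted for. That is true, but change scores do nothing for time since stroke, and they fix the coefficient on baseline rather than estimate it.

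Fourth, a reader might infer that allocation is unstratified. The documents do not support that: the isolated web address suggests that surrounding randomisation text was lost from this copy. In any case, unstratified allocation followed by covariate adjustment is valid.

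**Conclusion.** The point holds as one about which analysis decides. With 15 per arm and deliberately broad entry criteria, the lead test is the one least able to cope with an unlucky allocation, and the plan leaves open whether it or an unspecified adjusted analysis carries Aim 1. When the arms differ by more than 0.5 SD on a prognostic factor, which happens 17% of the time for a given pair, the unadjusted test rejects a true null in about 8% to 18% of cases, against about 5% for ANCOVA.

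The gain in precision depends on R²: almost none at 10%, and equivalent to about 23 instead of 15 patients per arm at 40%. The simpler formula 15/(1 − R²) would suggest 17 to 25, but it ignores the cost of estimating three covariates. At the low end the case rests on conditional error and on closing the choice of model, not on precision.

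The correlations, R², the share of early patients, alpha and power are all assumptions, since the documents give none. The simulations also assume normal covariates and linear effects.

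**What to change.** State one primary model for Aim 1 and Sub Aim 1.1: an ANCOVA or a mixed model, fitted to all 45 patients, with treatment group and three named covariates (baseline JTHF, time since stroke and baseline Fugl-Meyer). Take the Aim 1 contrast and the two placebo contrasts from that model. Give the form in which time since stroke enters. Keep the Student's t-test as a supporting analysis, and make the Aim 1 and sub-aim paragraphs describe the same analysis.

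Fix this before unblinding. It should not wait for the end of the trial, because the Blinding Questionnaire item allows subjects to be told their stimulation when their own participation ends.

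No patients, visits or measurements are added: both scores are in the planned assessments, and time since stroke is needed for eligibility. The cost is 3 degrees of freedom (42 to 39 in the three-arm model) and the assumption of common slopes and residual variance across arms. The change applies equally to patients already randomised.

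Separately, the sponsor should be asked whether the allocation list is stratified by time since stroke. If it is, the stratification factor should also be reflected in the model.

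### rTMS allocation can be disclosed subject by subject before the trial ends; this is a small, cheaply avoided risk to the blinding of later judgement-based ratings

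*Combined protocol and SAP*

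**What the plan says.** The Study overview states: "This study is a parallel, randomized, double blind, placebo controlled clinical trial". The three groups are "1) fluoxetine + active rTMS, 2) fluoxetine + sham rTMS or 3) sham rTMS + placebo fluoxetine", and the totals are fixed: "With a total of 45 patients, 15 patients will be randomized to each group using a computer based randomization program". Active rTMS occurs in one arm only, always with fluoxetine.

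Two provisions release rTMS allocation.

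- **Open label (Protocol Details).** "The 30 subjects randomized to receive sham rTMS will have the opportunity to enroll into an open label at the conclusion of their participation"; the participation meant is that in the randomized phase. On what the open label involves, the section adds: "This will consist of 10 daily active stimulation sessions that can be carried out over the course of 2 weeks".
- **Disclosure on request (Clinical Assessments, item 11, Blinding Questionnaire).** If a subject wants to know which stimulation was given, "the co-investigator may inform the subject when his/her participation in the trial has ended".

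On raters, Clinical Assessments opens with "A rater blind to the treatment arm will administer the following". Item 11 has the rater and the subject guess rTMS status, with a confidence score, after the daily sessions and again after the weekly sessions.

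**The concern.** Both provisions are triggered by the individual subject's end of participation. Neither is tied to the last subject's visit 22 or to data lock. An open-label offer identifies a sham subject, and the absence of an offer identifies an active one, whether or not the offer is taken up. Learning that a subject was active also reveals the drug, since every active-rTMS subject receives fluoxetine. Learning sham does not, because the sham subjects split 15 fluoxetine and 15 placebo.

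If 45 patients are enrolled over time, some will still be under assessment when others finish. Staff who learn earlier allocations could use them in two ways: to see which side effects and responses went with which coil, and to count down the known totals. If such knowledge reached a rater, outcomes that rest on judgement would be exposed, chiefly Fugl-Meyer (the secondary outcome for Aim 1) and the Modified Ashworth Scale. The primary outcome, the Jebsen-Taylor test, is timed and so less exposed.

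**Working it through.** **Plan's own figure.** 45 / 3 = 15 per arm. Sham rTMS = 45 − 15 = 30, which matches the 30 in Protocol Details. With no information the best guess is always sham, and it is right 30/45 = 66.7% of the time.

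**Step 1: how far counting down helps.** Assume the guesser knows every earlier allocation. With r places left in the list or block, of which a are active, the chance that the next subject is active is p = a/r, and the best guess is right with probability max(p, 1 − p). Average this over all orderings and positions. The documents give no block size, so the block sizes below are assumptions.

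| Scheme | Correct guesses | Allocations known for certain, of 45 |
|---|---|---|
| No information | 66.7% | 0 |
| One shuffled list of 45 | 68.5% (74.4% over the last 10 subjects) | 2.4 |
| Blocks of 15 | 71.0% | 6.4 |
| Blocks of 9 | about 73% | 9.6 |
| Blocks of 3 | 77.8% | 20 |

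The block-of-3 case can be checked by hand. The first place is guessed right 2/3 of the time. The second is right with probability 1/3 × 1 + 2/3 × 1/2 = 2/3. The third is certain. The mean is (2/3 + 2/3 + 1)/3 = 7/9 = 77.8%.

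**Step 2: incomplete knowledge.** If the two most recent earlier subjects are not yet disclosed, the list of 45 gives 67.4%, blocks of 9 give 68.1% and blocks of 3 fall back to 66.7%. If subjects finish in enrolment order, all earlier subjects have finished by a given subject's final rating. The table is then the relevant upper bound at that time point, but it still assumes that every allocation reaches the guesser.

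**Step 3: effect on the error rate.** The documents state no significance level and no SD. Assume a two-sided 5% Student's t-test, 15 against 15 (28 degrees of freedom), and a rater who shifts the score by 0.2 SD only when guessing active. Ties are guessed at random. The mean between-arm shift is

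d = 0.2 × [P(guess active | active) − P(guess active | sham)],

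and the noncentrality is d × √(15/2).

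- List of 45: d = 0.2 × (0.117 − 0.031) = 0.017 SD; noncentrality 0.047; error rate 5.0%.
- Blocks of 9: d = 0.2 × (0.318 − 0.068) = 0.050 SD; noncentrality 0.137; error rate 5.2%.
- Blocks of 3: d = 0.2 × (0.500 − 0.083) = 0.083 SD; noncentrality 0.228; error rate 5.6%.

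For comparison, shifting every active subject and no comparator subject gives d = 0.2, noncentrality 0.548 and an error rate of 8.3%. That is complete unblinding, not what these guess rates produce.

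The other route, learning from which effects went with which coil, cannot be quantified from the documents.

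**The case against.** The strongest reply is that the roles are already separated on paper. The rater is stated to be blind, the co-investigator is the one who discloses, and the subject is the one told. Nothing in the text has a rater make the offer, run open-label sessions or hear an allocation. Open-label entry is optional and disclosure depends on the subject's interest, so knowledge of every earlier allocation is a worst case. The blinding questionnaire could show a loss of blinding, although it would not prevent one. The available text is also incomplete: the visit table is not shown and the randomization material survives only as a web address. Handling rules may exist elsewhere.

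Most of this stands. It rules out two stronger readings that a reader might infer. The first is that later ratings do lose their blinding. The documents show only that release is permitted on a rolling basis and that, in the text available, no safeguard is spelled out beyond the statement that the rater is blind. The second is that a 0.2 SD rating shift would take a 5% error rate to 8.3%. That needs every active subject to be recognised and no sham subject mistaken for active, which not even the block-of-3 case delivers.

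The reply does not remove the timing rule itself. Both provisions plainly operate at each subject's own end of participation.

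**Conclusion.** The point holds as a minor design weakness. The plan permits rTMS allocation to be disclosed subject by subject in a trial described as double blind, and neither provision waits for the last rating. The disclosed subject's own randomized-phase ratings and blinding questionnaires are complete by then and are not biased.

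The size is small. Counting down fixed totals raises correct guesses from 66.7% to at most 68.5% without blocks, and to 78% under an assumed block size of 3. The matching error rates are about 5.0% to 5.6%. These figures rest on a rater who knows every earlier allocation and the block size, an assumed 0.2 SD shift, and an assumed two-sided 5% test. That other subjects are still being rated when disclosure happens is inferred, because accrual timing is not given. A change is worth making because it is cheap, not because harm has been shown. Confidence that the risk would materialise is low.

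**What to change.** Amend Blinding Questionnaire item 11 so that disclosure on request takes place only after the last subject's visit 22 and data lock.

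In Protocol Details, state that the sham-only offer and the open-label sessions are handled by existing staff who are already unblinded or who do no rating or enrolment. State also that raters and enrolling staff are not told who was offered or took part until data lock. The documents do not say who places the coil or who knows the allocation, so the sponsor must name the role. If this separation already exists in practice, one sentence recording it settles that part.

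The cost is a few sentences and a handling rule. Subjects who ask will wait longer for a direct answer. The sham-only offer will still reveal the arm to the subject, so the change protects later ratings and does not keep finishers blind.
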